**Schedule of Analyses:**

Data cuts for publication purposes will be performed until all subjects have completed the study, which is defined as the time point when the last enrolled subject has had the opportunity for five year for overall survival (OS) follow-up.

The final analysis will be performed when all subjects have completed the study.

**2 STUDY DESCRIPTION**

**2.1 Study Design**

This is a Phase 3b/4 safety study of nivolumab monotherapy for the treatment of patients with advanced or metastatic RCC. Approximately 180 subjects will be screened to determine eligibility within 28 days prior to first dose. Approximately 150 eligible subjects will be treated every 2 weeks with 240 mg nivolumab, intravenously over 30 minutes ( $\pm 5$  minutes). Each 28 day dosing period will constitute a cycle.

Subjects will be enrolled into 1 of 3 treatment groups as follows:

- Group 1: Subjects with predominant clear cell histology: 75 subjects (approximate)
- Group 2: Subjects with non-clear cell histology: 50 subjects (approximate, with a minimum of 50 subjects with non-clear cell histology)
- Group 3: Subjects with brain metastases regardless of histology: 25 subjects (approximate).

Note: If enrollment of 25 patients with brain metastases cannot be reached, the number of patients with non-clear cell (preferred) or clear cell histology group will be increased.

Subjects who are found on screening computed tomography (CT)/ magnetic resonance imaging (MRI) to have brain metastases will be enrolled to Group 3, if they do not require active treatment (radiation treatment/corticosteroids). Subjects who are found on screening CT/MRI to

[figure not shown]
have brain metastases that require immediate treatment with radiation treatment/corticosteroids will be re-enrolled to Group 3 after completing active treatment. Subjects who develop brain metastases while on treatment with nivolumab will not be re-assigned to Group 3 but will remain in the group assigned at enrollment

After screening and enrollment, subjects will be treated for a maximum of 24 months or until confirmed progression, unacceptable toxicity, withdrawal of consent, or the study is discontinued by the sponsor. Study treatment can continue beyond initial investigator assessed progression. The study will close after the last enrolled subject completes 5 years of follow up from the date of first treatment.

Subjects treated in the study who continue to derive benefit from the study treatment after 24 months of treatment or subjects who have not completed 24 months of treatment at discontinuation of the study by the Sponsor, should continue to be treated according to standard of care following completion of the study.

The study design schematic is presented in Figure 1.

**Figure 1: Study Design Schematic**

The study will continue until the last enrolled subject completes 5 years of follow up from the date of first treatment (LPFT).

## 2.2 Treatment Assignment

After the subject’s eligibility is established and informed consent has been obtained, the subject will be enrolled and a number will be assigned through an interactive voice response system (IVRS). Since this is a single arm study, all enrolled subjects who meet eligibility criteria will be treated with nivolumab at 240 mg IV every 2 weeks.

## 2.3 Blinding and Unblinding

Not applicable.

## 2.4 Protocol Amendments

This SAP incorporates the following protocol amendments.

**Table 2: Protocol Amendments**

Amendments	Date of Issue	Summary of Major Changes
Global Amendment 02	30-Apr-2016	
 
• Eligibility changes:                             
 
◆ Patients with previous treatment with mTOR inhibitor for clear-cell RCC histology are now eligible
 
◆ Patients with non-clear cell histology with up to 3 rather than 2 prior systemic treatments are now eligible
 
◆ Patients with non-clear cell RCC histology will now include collecting duct and medullary RCC (Appendix 4 updated).
 
 
 
• New protocol section (Section 5.6.2) for additional research that may be conducted on specimens already collected from subjects added.
 

Global Amendment 01	02-Oct-2015	
 
• The title of the study has been revised to reflect changes in the study population.
 
• The term immune-mediated adverse events (IMAEs), replaces the term select adverse events for consistency with nivolumab program.
 
• Total enrollment has been changed to 150 subjects from 250 subjects, with a maximum enrollment of 75 subjects with predominant clear cell histology and approximate enrollments of 50 subjects for non-clear cell and 25 subjects with brain metastases (either histology).
 
• Prior systemic treatments for subjects with non-clear cell histology may include treatment with mechanistic target of rapamycin (mTOR) inhibitor. Subjects with non-clear cell histology who otherwise qualify are eligible with no prior systemic treatment.
 
• Immune-related Response Criteria (irRC) has been removed from the protocol and is no longer an assessment of efficacy.
 
• [REDACTED]
 
• Nivolumab will be administered to all enrolled
 

**Table 2: Protocol Amendments**

Amendments	Date of Issue	Summary of Major Changes
		
subjects at a dose level of 240 mg IV every 2 weeks, replacing 3 mg/kg IV every 2 weeks as the dose for all enrolled subjects.
 

• The steroid treatment and taper for brain edema is now specified in protocol Section 3.4.3, Permitted Therapies.

• The FACT-G assessment tool will not be administered in this study.

• Papillary Renal Cell Carcinoma subtype is specified in protocol Appendix 4.

• Appendices of the original protocol have been renumbered to reflect the deletion of irRC (Appendix 2 in original protocol) and the addition

**3 OBJECTIVES**

**3.1 Primary**

To assess the incidence of high grade (CTCAE v4.0 Grade 3-4 and Grade 5) IMAEs in subjects with advanced or metastatic RCC who are treated with nivolumab monotherapy.

**3.2 Secondary**

To characterize the outcome of all high grade (CTCAE v4.0 Grade 3 4 and Grade 5) IMAEs in subjects with advanced or metastatic RCC who are treated with nivolumab monotherapy.

[Redacted content]

█ [REDACTED]

█ [REDACTED]

#### 4 ENDPOINTS

##### 4.1 Primary Endpoint(s)

The primary objective of the study will be assessed by measuring the incidence for high grade (Grade 3-4 and Grade 5) IMAEs.

The IMAEs are the following: skin, endocrinopathy, gastrointestinal, hepatic, renal, pulmonary, and neurologic adverse events.

##### 4.2 Secondary Endpoint(s)

The secondary objective of the study will be assessed by measuring the following:

- median time to onset, median time to resolution of high grade (Grade 3-4 and Grade 5) IMAEs
- percentage of subjects who received immune modulating medication (e.g. corticosteroids, infliximab, cyclophosphamide, Intravenous Immune Globulin [IVIG], and mycophenolate mofetil), or hormonal replacement therapy, the percentage of subjects who received  $\geq 40$  mg prednisone equivalents, total duration of all immune modulating medications given for the IMAE and summary of subjects with resolution of AEs after initiating these therapies.

█ [REDACTED]

█ [REDACTED]

█ [REDACTED]

█ [REDACTED]

[REDACTED]

[REDACTED]

[REDACTED]

[REDACTED]

[REDACTED]

[REDACTED]

## 5 SAMPLE SIZE AND POWER

Approximately 150 subjects will be treated with nivolumab in this study. This sample size will allow for estimating an incidence rate of 0.67% (n=1 subject with events) with a 95% CI (confidence interval) of (0.02%, 3.7%), or an incidence rate of 2% (n=3 subjects with events)

with a 95% CI of (0.4%, 5.7%). Furthermore, the sample size will allow for enough events to compare incidence with historical adverse event data.

## **6 STUDY PERIODS, TREATMENT REGIMENS AND POPULATIONS FOR ANALYSES**

### **6.1 Study Periods**

#### **6.1.1 Baseline Period**

Baseline evaluations or events will be defined as evaluations or events that occur before the date and time of the first dose of study treatment.

In cases where the time (onset time of event or evaluation time and dosing time) is missing or not collected, the following definitions will apply:

- Pre-treatment AEs will be defined as AEs with an onset date prior to but not including the day of the first dose of study treatment
- Baseline evaluations (laboratory tests, pulse oximetry and vital signs) will be defined as evaluations with a date on or prior to the day of first dose of study treatment

If there are multiple valid assessments, the last assessment prior to the first dose of study treatment will be used as the baseline in the analyses. If multiple assessments are collected at the same date (and time if collected), the assessment with the latest database entry date (and time if collected) will be considered as baseline.

#### **6.1.2 Post-baseline period**

On-treatment AEs will be defined as AEs with an onset date-time on or after the date-time of the first dose of study treatment (or with an onset date on or after the day of first dose of study treatment if time is not collected or is missing). For subjects who are off study treatment, AEs will be counted as on-treatment if the event occurred within 30 days (or 100 days depending on the analysis) of the last dose of study treatment. No “subtracting rule” will be applied when an AE occurs both pre-treatment and post-treatment with the same preferred term and grade.

On-treatment evaluations (laboratory tests, pulse oximetry, and vital signs) will be defined as evaluations taken after the day (and time, if collected and not missing) of first dose of study treatment. For subjects who are off study treatment, evaluations should be within 30 days (or 100 days depending on the analysis) of the last dose of study treatment.

Late emergent drug-related AEs will be defined as drug-related AEs with an onset date greater than 100 days after the last dose of study treatment in subjects off study treatment.

### **6.2 Treatment Regimens**

All subjects will be treated with nivolumab.

### **6.3 Populations for Analyses**

- **All enrolled subjects:** all subjects who signed an informed consent form and were registered into the interactive voice response system (IVRS).

- **All treated subjects:** all subjects who received any dose of nivolumab. This is the primary population for safety and efficacy analyses. Subpopulation analyses will be conducted for subjects in Groups 1-3.
- **All response evaluable subjects:** all treated subjects who have baseline and at least one on-study evaluable tumor measurement.
- **All PD-L1 tested subjects:** all subjects who had a tumor biopsy specimen available for assessment of PD-L1 expression.

## **7 STATISTICAL ANALYSES**

### **7.1 General Methods**

Unless otherwise noted, the bulleted titles in the following subsections describe tabulations of discrete variables, by the frequency and proportion of subjects falling into each category. Percentages given in these tables will be rounded and, therefore, may not always sum to 100%. Continuous variables will be summarized using the mean, standard deviation, median, minimum and maximum values.

Time to event distribution will be estimated using Kaplan Meier techniques. This will be done for endpoints PFS-1, OS and DOR. Median survival time along with 95% CI will be constructed based on a log-log transformed CI for the survivor function  $S(t)^{4,5}$ . Rates at fixed time points will be derived from the Kaplan Meier estimate and corresponding confidence interval will be derived based on Greenwood formula for variance derivation and on log-log transformation applied on the survivor function  $S(t)^7$ .

### **7.2 Study Conduct**

#### **7.2.1 Accrual**

The following will be presented on the enrolled population:

- Number of subjects accrued by country and investigational site
- Number of subjects accrued by month.

A by-subject listing of accrual and a by-subject listing of eligibility criteria will be produced.

#### **7.2.2 Relevant Protocol Deviations**

The following programmable deviations will be considered as relevant protocol deviations. A table summarize the relevant protocol deviations will be present.

##### **Eligibility:**

- Subject having a baseline Karnofsky Performance Status less than 70%.

##### **On-Study:**

- Subject not discontinuing study therapy upon evidence of further progression, defined as an additional 20% or greater increase in tumor burden from time of initial progression (including all target lesions and new measurable lesions).

A by subject listing will be produced.

### **7.3 Study Population**

#### **7.3.1 Subject Disposition**

The total number of subjects enrolled (treated or not) will be presented along with the reason for not being treated.

Number of subjects who discontinued treatment along with corresponding reason will also be tabulated.

A by-subject listing of pre-treatment subject status and a by-subject listing of end of treatment subject status will be produced.

#### **7.3.2 Demographics and Other Baseline Characteristics**

Descriptive statistics will be summarized the following baseline characteristics for all treated subjects.

- Age (descriptive statistics) ; Age (<65, ≥65 and <75, ≥ 75, ≥ 65)
- Gender, Race/Ethnicity, Region
- Karnofsky Performance Status (<70, 70, 80, 90, 100%)
- Height, weight, baseline ECG
- Enrollment Group (1, 2, 3)
- Histology (Clear Cell RCC, Non-Clear Cell RCC)
- Brain metastases (yes/no)
- All lesions: sites of diseases, number of disease sites per subject
- Presence of target lesions, measurement of largest target lesion, sum of reference diameter, site of target lesion, procedures for evaluating target lesion
- Baseline PD-L1 expression
- Baseline MSKCC risk group (Favorable, Intermediate, Poor)

By-subject listings of demographics, ECG, physical measurements, baseline disease characteristics will be provided.

#### **7.3.3 Medical History and Pretreatment Events**

Pretreatment events will be summarized by worst CTC grade (grade 1, 2, 3, 4, 5, unknown) by system organ class (SOC)/ preferred term (PT) for all treated subjects.

General medical history will be listed by subject.

#### **7.3.4 Prior Therapy Agents**

The following will be summarized:

- Number of prior systemic regimens received in advanced/metastatic setting (0, 1, 2, 3, >3)
- Number of prior systemic regimens with anti-angiogenic agent received in advanced/metastatic setting (0, 1, 2, > 2)
- Prior systemic regimen with cytokine agent in advanced/metastatic setting (yes or no)

- Prior systemic regimen with FDA approved VEGF TKI agent in advanced/metastatic setting (yes or no)
- Prior adjuvant or neo-adjuvant therapy (yes/no)
- Prior surgery related to cancer (yes or no)
- Prior radiotherapy (yes or no)
- Prior systemic therapy classified by therapeutic class and generic name.
- Prior/current other medication classified by anatomic and therapeutic classes.

Medication will be reported using the generic name. Listings of prior systemic cancer therapy, prior radiotherapy and prior surgery related to cancer, prior/current medications by subject will also be provided.

### 7.3.5 Baseline Examinations

Subjects with abnormal baseline physical examination will be tabulated by examination criteria. A listing of physical examination abnormal findings by subject will also be provided.

## 7.4 Extent of Exposure

Analyses in this section will be performed in all treated subjects.

### 7.4.1 Administration of Study Therapy

The following parameters will be summarized (descriptive statistics) by treatment arm:

- Relative dose intensity (%) using the following categories: < 50%; 50 - < 70%; 70 - < 90%; 90 - < 110%; ≥ 110%.
- Number of doses received (summary statistics)
- Cumulative dose
- Duration of treatment: duration of treatment will be presented using a Kaplan-Meier curve whereby the last dose date will be the event date for subjects who discontinued study therapy. Subjects who are still on study therapy will be censored on their last dose date.

A by-subject listing of extent of exposure: weight, number of doses, date of first and last dose, cumulative dose, relative dose intensity, duration of treatment, and reason for discontinuation

**Table 3: Administration of study therapy: definition of parameters**

nivolumab	
Dosing schedule per protocol	240 mg every 2 weeks
Dose	Dose (mg) is defined as Total Dose administered (mg) at each dosing date is collected on the CRF.
Cumulative Dose	Cum dose (mg) is sum of the doses (mg) administered to a subject during the treatment period.
Relative dose intensity (%)	$Cum\ dose\ (mg) / [(Last\ dose\ date - Start\ dose\ date + 14) \times 240 / 14] \times 100$
Duration of treatment	$Last\ dose\ date - Start\ dose\ date + 1$

## **7.4.2 Modifications of Study Therapy**

### **7.4.2.1 Dose Delays**

A dose will be considered as actually delayed if the delay is exceeding 2 days (i.e., greater than or equal to 3 days from scheduled dosing date). It is defined as (duration of previous cycle in days - 14). Dose delays will be divided into following categories: 3-7 days, 8-14 days, 15-42 days, >42 days. Reason for dose delay will be retrieved from CRF dosing pages.

The following parameters will be summarized:

- Number of dose delays per subject, Length of Delay and Reason for Dose Delay
- Number of subjects with at least one dose delay along with reason for dose delay.

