Archived Tumor Tissue or Recent Tumor Biopsy	X	One formalin-fixed paraffin embedded tumor tissue block, or 15 minimum FFPE unstained slides are to be submitted, if available. Submit a copy of the original pathology report along with the sample. Tissue samples from different biopsy procedures are to be submitted if available with each matching pathology report and biopsy date. Tissue sample from the metastatic tumor can be submitted if the primary tumor tissue is not available.

Table 5.1-2: On-Study Procedural Outline (CA209374)				
Procedure	Each Cycle Day 1	2nd Dose of Cycle	Q 8 wks from Day 1 Cycle 1	Notes
Safety Assessments				
Targeted assessments	X			Cycle 2 and beyond. Assessments within 48 hrs prior to dosing to include: Targeted physical exam, performance status and weight. Oxygen saturation by pulse oximetry at rest and after exertion for patients who complain of dyspnea or other respiratory symptoms
Adverse Events Assessment	Continuously assessed using NCI CTCAE v. 4.0.			
Concomitant Medications	X	X		
Laboratory Tests	X			Cycle 2 and beyond: (within 72 hrs prior to dosing) CBC w/differential, LFTs, BUN or serum urea, creatinine. TSH (reflex to free T3 and free T4 if abnormal result).
		X		LFTS only (within 72 hours prior to dosing)
Pregnancy Test	X			
Efficacy Assessments				
Radiographic Tumor Assessments			X	At Week 8 ( $\pm$ 1 week) and every 8 weeks $\pm$ 1 week thereafter, regardless of dosing schedule for the first 13 months then every 12 weeks $\pm$ 1 week until progression or treatment discontinuation whichever occurs later. Subjects with a history of brain metastasis perform surveillance CT/MRI approximately every 12 weeks, or sooner if clinically indicated.

Table 5.1-2: On-Study Procedural Outline (CA209374)				
Procedure	Each Cycle Day 1	2nd Dose of Cycle	Q 8 wks from Day 1 Cycle 1	Notes
Clinical Drug				
Administer Study Treatment	X	X		All subjects start treatment on C1D1 and continue treatment every 2 weeks for a maximum of 24 months or until confirmed progression, unacceptable toxicity, withdrawal of informed consent or discontinuation of the study by the Sponsor. Treatment for all subjects can continue beyond initial investigator-assessed progression. Drug administration is +/- 2 days but no less than 12 days from previous dose. Study drug infusion start and stop times will be recorded.
Other				

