### **7.4.2.2 Dose Reductions/Escalations and Infusion Interruption**

There will be no dose escalations or reductions of nivolumab allowed. Subjects may be dosed no less than 12 days from the previous dose.

Nivolumab infusion can be interrupted and/or the IV infusion rate can be reduced. This information will be retrieved from CRF dosing pages.

The following will be summarized:

- Number of subjects with at least one infusion with iv rate reduced along with the reason of the rate reduction and number of infusions with IV rate reduction per subject
- Number of subjects with at least one dose infusion interrupted along with the reason for the interruptions and number of infusions interrupted per subject

A by subject listing of study drug administered will be provided. A batch listing number will be also provided.

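### The SAP's dose-delay formula subtracts 14 days from a cycle, which the SAP defines as 28 days; it needs the interval between consecutive doses

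*SAP*

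**What the plan says.** SAP section 7.4.2.1 gives two statements about delay, one after the other. The first sets the counting rule, measured from the day on which the dose was due: "A dose will be considered as actually delayed if the delay is exceeding 2 days (i.e., greater than or equal to 3 days from scheduled" (the sentence ends by naming that day). The second gives the derivation: "It is defined as (duration of previous cycle in days - 14", with the bracket closed after the 14. The categories follow: "Dose delays will be divided into following categories: 3-7 days, 8-14 days, 15-42 days, >42 days". The section then lists the summaries that use these values: delays per subject with their length and reason, and subjects who had a delay, with the reason.

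SAP section 2.1 defines the term used in the formula: "Each 28 day dosing period will constitute a cycle". Protocol section 3.1 defines it in the same way. Protocol Table 5.1-2 is laid out accordingly, with one column for day 1 of each cycle and another for the second dose of the cycle.

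The dosing interval is stated separately. SAP Table 3 gives the schedule as "240 mg every 2 weeks" and uses 14 days in the relative dose intensity formula. On timing, Protocol Table 5.1-2 says "Drug administration is +/- 2 days but no less than 12 days from previous dose", and SAP section 7.4.2.2 says "Subjects may be dosed no less than 12 days from the previous dose".

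**The concern.** The constant 14 belongs to the interval between two doses, while the word cycle belongs to a 28-day period containing two doses. Combining them gives a rule that returns a delay of two weeks when nothing was late. The two sentences in section 7.4.2.1 then disagree about an on-time dose: 0 days under the first, 14 days under the second. The SAP sections available do not redefine a cycle as 14 days, and section 7.4.2.1 gives no separate formula for the scheduled dosing date to fall back on. A programmer must therefore either follow the formula and contradict the counting rule, or set aside a defined term without any written authority.

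On the literal reading there is a second defect. One value per 28-day cycle cannot show which of the two doses was late.

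What is at stake is the set of dose-delay summaries. No dose reductions are allowed, so delays are one of the main ways in which tolerability shows in the exposure data of this safety trial.

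**Working it through.** The plan states no numerical result to reproduce here; the item is a derivation rule. The check evaluates the rule under each reading of the word cycle and places the results in the SAP's own categories.

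**Inputs**

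- Formula: length of the previous cycle minus 14 days (SAP 7.4.2.1).
- Counted as delayed from 3 days; categories 3-7, 8-14, 15-42 and >42 days (SAP 7.4.2.1).
- Cycle length: 28 days (SAP 2.1, Protocol 3.1).
- Dosing interval: 14 days (SAP Table 3).
- Dosing window: ±2 days (Protocol Table 5.1-2), with at least 12 days between doses (same table and SAP 7.4.2.2).

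**Step 1. Literal reading: cycle length minus 14, with a cycle of two doses**

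| Cycle length (days) | Formula result (days) | Category |
|---|---|---|
| 24 (12 + 12, the minimum spacing) | 10 | 8-14 |
| 26 | 12 | 8-14 |
| 27 | 13 | 8-14 |
| 28 (on time) | 14 | 8-14 |
| 29 | 15 | 15-42 |
| 30 | 16 | 15-42 |
| 56 | 42 | 15-42 |
| 57 | 43 | >42 |

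Every row exceeds the 3-day threshold, including the shortest cycle that the minimum spacing permits. A cycle that runs d days over 28 is reported as d + 14. Late shifts of 1 or 2 days move into 15-42 days; early shifts stay in 8-14 days.

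**Step 2. Scheduled-date rule in the preceding sentence**

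An on-time dose is 0 days from its scheduled date. Since 0 < 3, it is not counted. This contradicts the 28-day row of step 1.

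**Step 3. Interval reading: days between consecutive doses minus 14**

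| Interval (days) | Result (days) | Category |
|---|---|---|
| 12 | -2 | not delayed |
| 14 | 0 | not delayed |
| 16 | 2 | not delayed |
| 17 | 3 | 3-7 |
| 21 | 7 | 3-7 |

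The first counted delay is at 17 days, one day beyond 14 + 2. Threshold, window and categories all fit this reading.

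**Step 4. Cross-check against relative dose intensity**

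SAP Table 3 divides the cumulative dose by (last dose date - first dose date + 14) × 240/14. For k on-time doses this is 240k / {[14(k - 1) + 14] × 240/14} = 240k / 240k = 100%. The same SAP would therefore report 100% intensity for a subject whom the literal delay formula counts as delayed in every cycle. The SAP already treats 14 days as the dose-to-dose interval.

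**Step 5. Why the word should change, not the constant**

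Replacing 14 by 28 would remove the spurious two weeks but would net the two intervals within a cycle. Intervals of 12 and 18 days give 30 - 28 = 2, not counted, although the second dose came 18 - 14 = 4 days late relative to the one before it.

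**The case against.** The strongest reply is that section 7.4.2.1 should be read as a whole. Its first sentence takes a dose as the unit and the scheduled dosing date as the reference, so an on-time dose has no delay. The formula then describes that same delay, and the 28-day reading would contradict the sentence just before it. The constant 14 matches Table 3, and the 3-day threshold matches the ±2 day window. On this view the word cycle is loose wording for the dosing interval. That argument is persuasive about intent and stands. It does not make the formula correct: it shows that the formula gives the intended result only if a defined term is set aside.

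A reader might infer that the study's tables will report every on-time cycle as a 14-day delay, about 26 such cycles over 24 months (730.5/28 = 26.1). The documents do not support that. These false delays arise only if the formula is programmed literally on 28-day cycles, and nothing in the protocol or SAP shows that it was or will be.

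Nor do the documents show that reporting of toxicity-driven delays is lost. Adverse events leading to dose delay have their own section (SAP 7.6.6, which refers to the Core Safety SAP), and immune-mediated events leading to drug delay are tabulated under SAP 7.6.8.1. Neither is shown to depend on this formula. Reasons for delay come from the case report form.

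One further objection concerns the interval formula itself. On a fixed 14-day calendar, a dose given 2 days early and the next given 1 day late are both within the window, yet they lie 14 + 2 + 1 = 17 days apart and count as a 3-day delay. This is true, but it applies equally to the SAP's own formula on its intended reading. It is a reason to define the scheduled date explicitly.

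**Conclusion.** The concern holds as a wrong derivation rule of minor severity. The formula in SAP section 7.4.2.1 conflicts with the cycle definition in SAP section 2.1 and with the counting rule in its own section. Taken literally, it gives 14 days for an on-time cycle and 12 to 16 days for cycles of 26 to 30 days, all counted as delayed. Those figures assume literal programming and cycles that contain both doses.

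The evident intent is the interval between doses, and on that reading the rule behaves correctly. The summaries exposed are the number and length of delays and the number of subjects with a delay, all descriptive. The primary endpoint (incidence of high-grade immune-mediated events), the secondary endpoints (their timing and management), the sample size and the power do not use this formula.

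**What to change.** Replace the formula sentence in SAP section 7.4.2.1 with: Delay = (date of current dose - date of previous dose) - 14 days, computed for every dose after the first. Keep the 3-day threshold and the four categories.

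Also state there that, for this derivation, the scheduled dosing date is 14 days after the previous dose. This aligns the two sentences and settles how an early dose followed by a late one is counted.

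The change concerns the analysis derivation only and alters no dosing rule. It costs one replaced sentence and one clarifying phrase in the SAP. The dosing dates are already needed for the relative dose intensity and for the by-subject listing of study drug, so no new data are required. If the delay tables have already been programmed, confirm that the code uses the interval between doses.
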